2. INTRODUCTION

This SAP provides the detailed methodology for summary and statistical analyses of the data collected in study B7461024. This analysis plan is meant to supplement the study protocol. Any deviations from this analysis plan will be described in the Clinical Study Report.

The primary analysis will include all data up to a data cutoff date which will be determined by the data maturity and is currently estimated to be around 8 months after last subject first dose in study B7461024. All summaries and analyses will include all data pertaining to visits/assessments performed up to and including the data cutoff date.

2.1. Study Objectives

Primary Objective(s):

- To evaluate the anti-tumor effect of lorlatinib as a single agent as measured by objective response rate (ORR) per RECIST v1.1 in locally advanced or metastatic ALK-positive NSCLC patients whose disease has progressed after crizotinib treatment.

Secondary Objective(s):

- To evaluate the anti-tumor effect of lorlatinib as a single agent as measured by ORR per RECIST v1.1 in locally advanced or metastatic ALK-positive NSCLC patients whose disease has progressed after ALK inhibitor treatment other than crizotinib.
- To evaluate the progression-free survival (PFS) and overall survival (OS) in locally advanced or metastatic ALK-positive NSCLC patients whose disease has progressed after crizotinib and other ALK inhibitor treatment, respectively.
- To evaluate other antitumor activities in locally advanced or metastatic ALK-positive NSCLC patients whose disease has progressed after crizotinib and other ALK inhibitor treatment, respectively.
- To evaluate the safety and tolerability of lorlatinib treatment in locally advanced or metastatic ALK+ NSCLC patients whose disease has progressed after crizotinib and other ALK inhibitor treatment.
- To evaluate the pharmacokinetics of lorlatinib and potential pharmacokinetic/pharmacodynamics relationship for lorlatinib if appropriate.

CCI

2.2. Study Design

[figure not shown]
This is an open-label, multi-center, Phase 2, dual-cohort study of evaluating the efficacy and safety of PF-06463922 as a monotherapy in patients with ALK-positive locally advanced or metastatic NSCLC.

Approximately 100 patients with locally advanced or metastasis ALK-positive NSCLC will be enrolled to receive lorlatinib monotherapy. In Cohort 1 approximately 66 patients whose disease has progressed after crizotinib will be enrolled, and in Cohort 2, approximately 34 patients whose disease has progressed after ALK inhibitor other than crizotinib.

A cycle duration will be 3 weeks (21 days) and will always be considered 3 weeks irrespective of any dose delays/dosing interruptions or missed doses which may affect nominal days of each cycle.

The study design is illustrated in Figure 1 below.

Figure 1. Study B7461024 Design

Study treatment may continue until confirmed disease progression assessed by ICR, subject refusal, subject lost to follow-up, unacceptable toxicity, or the study is terminated by the sponsor, whichever comes first. Subjects who develop radiological disease progression confirmed by ICR assessment but are otherwise continuing to derive clinical benefit from study treatment will be eligible to continue with the treatment they have been assigned to, provided that the treating physician has determined that the benefit/risk for doing so is favorable.

3. ENDPOINTS AND BASELINE VARIABLES: DEFINITIONS AND CONVENTIONS

3.1. Primary Endpoint(s)

- Objective Response (OR) in patients whose disease have progressed after crizotinib (Cohort 1) by independent central radiology (ICR) assessment per RECIST v1.1. OR is defined as a complete response (CR) or partial response (PR) recorded from enrollment until disease progression or start of new anti-cancer therapy. Both CR and PR must be confirmed by repeat assessments performed no less than 4 weeks after the criteria for response are first met.

3.2. Secondary Endpoint(s)

- OR in patients whose disease have progress after ALK inhibitor treatment other than crizotinib (Cohort 2) as assessed by RECIST v1.1 per ICR assessment.

- Progression-free survival (PFS) based on ICR assessment and investigator assessment by RECIST v.1.1 is defined as the time from first dose to first documentation of objective disease progression or to death due to any cause, whichever comes first in both Cohort 1 and Cohort 2.

- Overall Survival (OS) is defined as the time from first dose to the date of death due to any cause.

- Intracranial objective response(IC-OR)

IC-OR is defined the same as OR, but limited to Intra Cranial lesions only on patients with CNS metastases (ie, Best Overall Intracranial Response as confirmed CR or confirmed PR considering only the lesions having disease site as Brain).

- Duration of response (DoR)

DoR is defined as the time from the first documentation of CR or PR to the first documentation of disease progression or death due to any cause, whichever occurs first.

- Duration of intracranial response(IC-DoR)

IC-DoR is defined the same as DoR, but limited to Intra Cranial lesions only on patients with CNS metastases (ie, Best Overall Intracranial Response as confirmed CR or confirmed PR considering only the lesions having disease site as Brain).

- Time to tumor response (TTR)

TTR is defined as the time from first dose to first documentation of objective tumor response (CR or PR).

- PK: parameters on day 1 of cycle 1 and at steady state: C_{max} , T_{max} , AUC_t , AUC_{tau} at steady state, AUC_{inf} , CL/F , Vz/F , $t_{1/2}$ and R_{ac} as data permit.

CCI

3.4. Baseline Variables

Any deviations from the protocol specified window will be documented as protocol deviations. A separate definition of adequate baseline will be provided for tumor assessment related efficacy endpoints.

For efficacy analyses, safety (including Eastern Cooperative Oncology Group (ECOG) performance status) and baseline characteristics associated with tumor assessments (eg, number of sites of disease at baseline), the last assessment prior to first dose will serve as the baseline assessment.

Triplicate ECGs are collected; therefore the baseline for each ECG measurement is the average of the pre-dose measurements on the baseline day. Unscheduled assessments will not be included in the calculation of the average. Most of the ECG parameters will not be derived as they are provided by sites on the CRF. QTcF (Fridericia's correction) and QTcB (Bazett's correction) will be derived based on RR and QT. The average of the replicate measurements will be determined after the derivation of the individual parameters at each timepoint.

3.5. Safety Endpoints

Safety endpoints will be summarized based on the on-treatment period unless otherwise specified.

On-treatment is defined as the time from the first dose of study treatment through the end of study follow-up (infinite lag) or start of new anti-cancer drug therapy, whichever occurs first. Adverse events occurring on the same day as the first dose of study treatment will be considered to have occurred during the on-treatment period. All other assessments which occur on the same day as the first dose of study treatment will be considered baseline assessments (see [Section 3.4](#) for the definition of baseline).

Safety data collected outside the on-treatment period as described above will be listed but not summarized.

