8.1.4. Time Period for Collecting AE/SAE Information

The time period for actively eliciting and collecting AEs and SAEs (“active collection period”) for each subject begins from the time the subject provides informed consent, which is obtained before the subject’s participation in the study (ie, before undergoing any study-related procedure and/or receiving investigational product), through and including a minimum of 28 calendar days after the last administration of the investigational product.

For subjects who are screen failures, the active collection period ends when screen failure status is determined.

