8.1.4.2. Recording Non-serious AEs and SAEs on the CRF

During the active collection period, both non-serious AEs and SAEs are recorded on the CRF.

Follow-up by the investigator may be required until the event or its sequelae resolve or stabilize at a level acceptable to the investigator, and Pfizer concurs with that assessment.

If a subject begins a new anticancer therapy, the recording period for non-serious AEs ends at the time the new treatment is started; however, SAEs must continue to be recorded on the CRF during the above-indicated active collection period.

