8.2.3. Serious Adverse Events

A serious adverse event is any untoward medical occurrence at any dose that:

- Results in death;
- Is life-threatening (immediate risk of death);
- Requires inpatient hospitalization or prolongation of existing hospitalization;
- Results in persistent or significant disability/incapacity (substantial disruption of the ability to conduct normal life functions);
- Results in congenital anomaly/birth defect.

Or that is considered to be:

- An important medical event.

Medical and scientific judgment is exercised in determining whether an event is an important medical event. An important medical event may not be immediately life-threatening and/or result in death or hospitalization. However, if it is determined that the event may jeopardize the subject or may require intervention to prevent one of the other AE outcomes, the important medical event should be reported as serious.

Examples of such events are intensive treatment in an emergency room or at home for allergic bronchospasm; blood dyscrasias or convulsions that do not result in hospitalization; or development of drug dependency or drug abuse.

Progression of the malignancy under study (including signs and symptoms of progression) should not be reported as an SAE unless the outcome is fatal within the active collection period. Hospitalization due to signs and symptoms of disease progression should not be reported as an SAE. If the malignancy has a fatal outcome during the study or within the active collection period, then the event leading to death must be recorded as an AE on the CRF, and as an SAE with Common Terminology Criteria for Adverse Events (CTCAE) Grade 5 (see the [Severity Assessment](#) section).

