9.5.1. Adverse Events

Adverse events will be classified using the medical dictionary for regulatory activities (MedDRA) classification system. The severity of the toxicities will be graded according to the NCI CTCAE v4.03 whenever possible (<http://ctep.info.nih.gov/reporting/ctc.html>).

The focus of AE summaries will be on Treatment Emergent Adverse Events (TEAE), those with initial onset or increasing in severity after the first dose of study medication. TEAE will be summarized by worst NCI CTCAE v4.03 severity grade and relatedness to study treatment corresponding to system organ class and MedDRA preferred term. The number and frequency of subjects who experienced any AE, serious AE (SAE), treatment-related AE and treatment-related SAE will be reported.

Adverse events leading to death or discontinuation of study treatment, events classified as NCI CTCAE v4.03 Grade ≥ 3 , study drug-related events, and serious adverse events will be considered with special attention.

Detailed information collected for each adverse event will be listed with a description of the event, duration, whether the adverse event was serious, intensity, relationship to study treatment, action taken, and clinical outcome.

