3.5.1. Adverse Events

An adverse event is considered treatment emergent (TEAE) if the event occurs during the on-treatment period.

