6.5.2. Deaths

The frequency (number and percentage) of patients in the safety analysis set who died and who died within 28 days after last dose of study treatment as well as the primary reason for death, will be tabulated based on information from the ‘Notice of Death’ and ‘Survival Follow-Up’ CRFs, by Cohort.

The frequency (number and percentage) of patients in the safety analysis set who died during follow-up period after 28 days after the last dose of study treatment will also be provided.

Date and cause of death will be provided in individual patient data listing together with selected dosing information (study treatment received, date of first/last administration, dose).

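### The SAP's open-ended TEAE window runs past the AE collection the protocol requires, so serious and Grade 5 rates mix two levels of ascertainment

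*SAP*

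**What the plan says.** The analysis side is in the SAP. Section 3.5 states: "On-treatment is defined as the time from the first dose of study treatment through the end of study follow-up (infinite lag"), with a second limit, "or start of new anti-cancer drug therapy, whichever occurs first". Section 3.5.1 then says: "An adverse event is considered treatment emergent (TEAE) if the event occurs during the on-treatment period". Section 6.5.1 bases adverse event analyses on treatment-emergent events by default, and its high-level summary has a serious row and a Grade 5 row. Section 6.5.2 separately counts patients "who died within 28 days after last dose of study treatment" and patients who died later.

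The collection side is in the protocol. Section 8.1.4 runs the active collection period from consent "through and including a minimum of 28 calendar days after the last administration of the investigational product". Section 8.1.4.2 adds: "During the active collection period, both non-serious AEs and SAEs are recorded on the CRF". After that period, section 8.1.4.1 has serious events reported once the investigator learns of them, and at a minimum those thought possibly drug related. In the Schedule of Activities the adverse event row extends into post-treatment follow-up but is empty in the survival follow-up column.

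Fatal cancer is covered twice in protocol 8.2.3. One sentence makes progression a reportable SAE only when it is fatal within the active collection period. A later sentence in the same paragraph reads: "If the malignancy has a fatal outcome during the study or within the active collection period, then the event leading to death must be recorded". That entry is to be both an AE and a Grade 5 SAE.

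**The concern.** A percentage of patients with an event is easy to interpret when every patient is watched in the same way throughout the window. Here the window can run for months or years beyond the last dose, while systematic collection is required only for its first part. In the later part, new non-serious events are not required to be collected, and serious events come in only when the investigator hears of them.

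Grade 5 is the sharpest case. Under the broader sentence of protocol 8.2.3, a cancer death many months after the last dose is a Grade 5 TEAE if the patient started no new anti-cancer drug. The same death after the start of a new drug falls outside the window. The Grade 5 percentage would then partly measure length of survival follow-up and access to later therapy, not events around lorlatinib exposure, and the Grade 5 row itself would not separate the two.

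**Working it through.** Setting the two sides next to each other for a patient who starts no new anti-cancer drug:

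| Time after last dose | What must be collected | Where it is counted |
|---|---|---|
| Up to at least 28 days | All AEs and SAEs (protocol 8.1.4, 8.1.4.2) | TEAE |
| After the active collection period, to end of follow-up | SAEs on awareness, at a minimum those possibly related (8.1.4.1); toxicities already continuing are followed at least every 4 weeks (Schedule of Activities, footnote 27) | TEAE |

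The SAP therefore gives one label to two kinds of data. That conclusion needs no numbers.

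**Size of the Grade 5 effect.** The documents give no TEAE or Grade 5 rate to reproduce, and none of the inputs below comes from them. All are assumptions:

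- follow-up per patient uniform between 8 and 24 months;
- exponential time on drug, median 6 or 12 months, with no deaths on drug;
- exponential survival after stopping, median 6 or 12 months;
- a share s of 30% or 60% never starts a new drug, and the rest start 1 month after stopping;
- every death inside the window is recorded as Grade 5 (the broader sentence of 8.2.3).

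Let A be the probability that a patient has died by the cutoff, B the probability of an observed death within 1 month of stopping, and C the same within 28 days (28/30.4375 = 0.92 month). Then

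Grade 5 rate, SAP window = s × A + (1 − s) × B

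Grade 5 rate, 28-day limit = C

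For follow-up f, with a and b equal to ln 2 divided by the median time on drug and the median survival after stopping, the probability of an observed death within d months of stopping is the integral from 0 to min(d, f) of b·exp(−bx)·[1 − exp(−a(f − x))] dx, averaged over f. For A, d is unlimited.

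| Median on drug / after stopping (months) | A | B | SAP window, s = 30% | SAP window, s = 60% | 28-day limit (C) |
|---|---|---|---|---|---|
| 6 / 6 | 53.4% | 8.8% | 22.2% | 35.5% | 8.2% |
| 6 / 12 | 35.9% | 4.5% | 13.9% | 23.3% | 4.2% |
| 12 / 6 | 35.9% | 6.3% | 15.2% | 24.0% | 5.8% |
| 12 / 12 | 23.8% | 3.2% | 9.4% | 15.6% | 3.0% |

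First row: 0.30 × 53.4 + 0.70 × 8.8 = 16.0 + 6.2 = 22.2; and 0.60 × 53.4 + 0.40 × 8.8 = 32.0 + 3.5 = 35.5. Mortality is identical in these two cases. Only the share starting no new drug differs, and the 28-day figure stays at 8.2%.

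**Growth with follow-up.** A second set of assumptions uses 12 months of accrual, median 12 months on drug, median survival after stopping of 4 or 8 months, and 30% to 80% starting a new drug 1 month after stopping. Cutoffs are counted from the last patient's first dose; SAP 2 expects about 8 months for the primary analysis.

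| Cutoff (months) | SAP window | 28-day limit |
|---|---|---|
| 8 | 9% to 29% | 4% to 8% |
| 24 | 18% to 55% | 6% to 12% |
| 36 | 22% to 65% | 7% to 13% |

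**The other reading.** If sites follow the narrower sentence of 8.2.3, cancer deaths after the active collection period are not recorded as Grade 5 events. Every late death in these scenarios is treated as a recorded cancer death, so the modelled gap between the two columns essentially closes. In practice, other fatal SAEs reported late would remain.

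**The case against.** The best case for the plan has five parts.

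- **Agreement with the protocol.** Protocol 9.5.1 describes TEAEs as "those with initial onset or increasing in severity after the first dose of study medication" and gives no upper limit. An open window is consistent with that, and it keeps late drug-related SAEs in the main tables. This stands: the open window breaks no protocol rule, and preferring a fixed lag is a judgement.
- **28 days is a minimum.** A reader might infer that adverse event collection stops at 28 days. The documents do not say so: the period is a minimum, the adverse event row continues into post-treatment follow-up, and continuing toxicity is followed until it resolves or no improvement is expected. What remains is that nothing requires new events to be collected systematically to the end of follow-up.
- **The Grade 5 figures depend on one sentence of 8.2.3.** This stands. CRF recording is also unsettled: section 8.1 has all SAEs on the CRF, while 8.1.4.2 describes recording during the active period.
- **Deaths are already split at 28 days in SAP 6.5.2.** That helps a careful reader, but the Grade 5 and serious TEAE rows are not split, so the tables can give different pictures.
- **A 28-day cap on everything would lose planned data.** A reader might infer that the whole on-treatment definition should be cut to 28 days. The Schedule of Activities places hematology, chemistry, lipids, coagulation, urinalysis, ECG and LVEF at 30 and 60 days after treatment, and the EOT visit may fall up to 4 weeks plus 1 week (35 days) after the last dose. SAP 3.5 lists but does not summarize data outside the window, so such a cap would drop scheduled visits. This objection stands in full for those data types.

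No between-cohort safety comparison is planned either, so a claim of biased cohort comparison would go too far. The point concerns how each rate is read.

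**Conclusion.** The mismatch is real and worth correcting for the adverse event tables. The mixing of two ascertainment levels in the serious and Grade 5 TEAE rates follows from the text alone. The dependence of Grade 5 on follow-up and later therapy is conditional: it arises under the broader sentence of protocol 8.2.3, and only through patients who have not started a new anti-cancer drug. Under that reading and the assumed inputs the rate is about 9% to 36%, against 3% to 8% with a 28-day limit. Under the narrower sentence most of the difference disappears. The documents do not show which sentence sites follow, so the range illustrates a possible effect and does not predict one. They also do not support replacing the open window for all safety data. The primary ORR analysis is unaffected.

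**What to change.** 1. Reconcile the two sentences in protocol 8.2.3 on fatal malignancy after the active collection period, so that all sites record such deaths in the same way.
2. In SAP 3.5 and 6.5.1, report the TEAE, serious and Grade 5 tables for first dose to the earlier of last dose + 28 days and the day before new anti-cancer drug therapy. Show later serious and Grade 5 events separately, as the infinite-lag version, so that late related SAEs stay visible.
3. Do not apply the 28-day limit to laboratory, ECG and LVEF summaries. Their window must still cover the EOT visit and the scheduled 30- and 60-day visits.

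The cost is SAP wording, one date derivation, one extra set of adverse event tables and a clarification of protocol 8.2.3. No new data are needed.

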6.5.3. Laboratory Data

Laboratory results will be converted to International System of Units (Système International d'unités, SI) units which will be used for applying toxicity grades and for all summaries.

As described in [Section 3.4](#), baseline will be defined as the last assessment performed on or prior to date of the first dose of study treatment. If there are multiple assessments that meet the baseline definition on the same day without the ability to determine which was truly last, then the worst grade will be assigned as the baseline grade. Since a few CTCAE terms (including Hypo/Hypercalcemia and Activated Partial Thromboplastin) can be derived using several laboratory tests (analytes) refer to the section 2.3.7 of the “Pfizer Oncology CTCAE Grading Implementation Guidance for Laboratory Data” for determination of baseline CTCAE grade in this situation.

Additionally, laboratory results will be programmatically classified according to NCI-CTCAE version 4.03 grade. Non-numerical qualifiers will not be taken into consideration in the derivation of grade (eg, hypokalemia Grade 1 and Grade 2 are only distinguished by a non-numerical qualifier and therefore Grade 2 will not be derived). In summary statistics the number and percentage of patients corresponding to grades that only include non-quantitative criteria will be displayed as a blank or NA (not assessed) rather than 0. If there is any overlap between grade criteria (eg, CTCAE grading criteria for Creatinine Increased - a value can fall into one range based on comparison to ULN and another range based on comparison to baseline), the highest (worst) grade would be assigned to that record. Grade 5 is defined in the CTCAE criteria guidance as an event with an outcome of death. Since laboratory data does not collect an outcome, Grade 5 is not used when programmatically grading laboratory data.

Grade 0 or Outside Toxicity Reference (OTR) is not defined specifically by in the CTCAE guidance. However, programmatically this is used as a category to represent those patients who did not meet any of the Grades 1 to 4 criteria. If the laboratory value is evaluable for CTCAE criteria grading (numeric value is present, valid units and ranges are present as required to allow conversion to standard units and grading), and does not qualify for any of the Grade 1-4 criteria for a given lab test, then the value is assigned as Grade 0 or OTR.

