6.5.5. Electrocardiogram

Triplicate ECGs were required at each assessment. A mean score is calculated for any replicate measurements having the same nominal visit. The mean measurement is reported.

ECG summaries will include all ECG assessments from the on-treatment period. All ECG assessments will be listed, and those collected outside the on-treatment period will be flagged in the listing.

The analysis of QT data is complicated by the fact that the QT interval is highly correlated with heart rate. Because of this correlation, formulas are routinely used to obtain a corrected value, denoted QTc, which is independent of heart rate. This QTc interval is intended to represent the QT interval at a standardized heart rate.

Fridericia's correction (QTcF) will be programmatically derived using the following formula:

$$QTcF(m\ sec) = QT(m\ sec) / \sqrt[3]{RR(sec)}$$

and Bazett's correction (QTcB) will be programmatically derived using the following formula:

$$QTcB(m\ sec) = \frac{QT(m\ sec)}{\sqrt{RR(sec)}}$$

where RR represents the RR interval of the ECG, in seconds.

RR used in the above formula will be derived by $(60/\text{HR (bpm)})$ if HR is collected. Otherwise, RR will be directly used for calculation.

Additionally QTcB and QTcF (and QTcS if applicable) will be summarized by maximum on-treatment values using the following categories:

- ≤ 450 msec;
- > 450 msec but ≤ 480 msec;
- > 480 msec but ≤ 500 msec;
- > 500 msec.

Unscheduled assessments will be utilized in addition to planned assessments.

Shift tables will be provided for baseline value versus worst on-treatment value.

Additionally maximum increases from baseline (including scheduled and unscheduled assessments) will be summarized based on the following categories:

- Change > 60 msec;
- Change > 30 msec but ≤ 60 msec;
- Change ≤ 30 msec.

In the event that neither Fridericia's nor Bazett's correction adequately adjusts for heart rate, an additional correction such as a population or patient-specific baseline correction could be used and should be fully justified.

For PR and QRS maximum increases from baseline, the following categories will be applied:

- PR change $\geq 50\%$ if absolute baseline value was < 200 msec;
- PR change $\geq 25\%$ if absolute baseline value was ≥ 200 msec;
- QRS change $\geq 50\%$ if absolute baseline value was < 100 msec,
- QRS change $\geq 25\%$ if absolute baseline value was ≥ 100 msec.

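### SAP 3.5's same-day rule, read literally, leaves the planned Cycle 1 Day 1 post-dose ECG out of both baseline and the on-treatment summaries

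*SAP*

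**What the plan says.** Five statements bear on the ECG taken 1-4 hours after the first dose.

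- **Protocol, Schedule of Activities, footnote 13.** On Cycle 1 Day 1, ECGs are planned before the dose and again 1-4 hours after it. Further 1-4 hour post-dose ECGs are planned on Cycle 1 Day 8, Cycle 1 Day 15 and Cycle 2 Day 1. From Cycle 3, every other cycle has a single pre-dose reading.
- **SAP 3.5, period.** "On-treatment is defined as the time from the first dose of study treatment", running to the end of follow-up or the start of a new anti-cancer drug, whichever is earlier.
- **SAP 3.5, same-day rule.** Adverse events on the day of first dose are on-treatment, but "All other assessments which occur on the same day as the first dose of study treatment will be considered baseline assessments". The sentence refers to SAP 3.4 for the definition of baseline. Then: "Safety data collected outside the on-treatment period as described above will be listed but not summarized".
- **SAP 3.4.** The general rule is that "the last assessment prior to first dose will serve as the baseline assessment". For ECGs, baseline is "the average of the pre-dose measurements on the baseline day".
- **SAP 6.5.5.** "ECG summaries will include all ECG assessments from the on-treatment period". Also: "All ECG assessments will be listed, and those collected outside the on-treatment period will be flagged in the listing".

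**The concern.** The same-day rule in SAP 3.5 works by calendar date, whereas the ECG baseline in SAP 3.4 works by time relative to dose. For most assessments the difference is harmless. The ECG is the only safety assessment explicitly scheduled after the dose on Cycle 1 Day 1, and there the two rules collide. A programmer who follows the explicit same-day sentence would keep the post-dose triplicate out of the on-treatment tables, and SAP 3.4 would keep it out of the baseline average. A programmer who follows the period definition would include it. The same SAP could therefore yield two different sets of safety tables.

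The outputs at stake are in SAP 6.5.5: categories of maximum on-treatment QTc, categories of maximum increase in QTc, PR and QRS, and the baseline-to-worst shift tables. PR matters most. Protocol 1.2.3.3.3 links higher plasma concentration to PR prolongation, while protocol 5.5.2 reports no impact on QRS or QT. Because scheduled on-treatment ECGs from Cycle 3 are pre-dose, the 1-4 hour post-dose window is covered only four times in the whole schedule.

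**Working it through.** The plan gives no figure to reproduce. The check is a classification of one time point, followed by a count of scheduled ECGs.

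**Classification of the Cycle 1 Day 1 1-4 hour post-dose triplicate**

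| Rule | Result |
|---|---|
| SAP 3.4, ECG baseline | Not part of baseline (pre-dose only) |
| SAP 3.5, same-day sentence | Baseline assessment by date, hence not on-treatment, hence listed only |
| SAP 3.5, period definition alone | On-treatment |
| SAP 6.5.5 | Summarised only if on-treatment |

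SAP 3.4 with the same-day sentence puts the triplicate in neither group. SAP 3.4 with the period definition puts it on-treatment. No ECG-specific exception that would choose between them appears in SAP 3.4, 3.5, 5.2.13, 5.3.4 or 6.5.5.

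The SAP's own use of 3.4 does not help. SAP 6.5.3 cites it for laboratory data as meaning that "baseline will be defined as the last assessment performed on or prior to date of the first dose of study treatment", a date-based rule, although 3.4 itself is worded relative to the first dose.

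**Share of scheduled ECG time points affected, on the literal reading**

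The inputs are footnote 13 and the ECG row of the Schedule of Activities (which adds end-of-treatment, 30-day and 60-day ECGs), 21-day cycles, the cutoff at about 8 months after last subject first dose (SAP 2), and 30.4375 days per month (SAP 5.2.14). Day 1 of Cycle k is study day 21 × (k − 1) + 1.

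- 1-4 hour post-dose time points: C1D1, C1D8, C1D15, C2D1 = 4. Share = 1/4 = 25%.
- All scheduled time points after first dose, patient stopping after Cycle 2: 4 + end of treatment + 30-day + 60-day = 7. Share = 1/7 = 14.3%. If the two follow-up ECGs are missed, or come after a new anti-cancer drug has started: 1/5 = 20%.
- Last-enrolled patient still on treatment at cutoff: 8 × 30.4375 = 243.5 days. Cycle 12 starts on day 232 and Cycle 13 on day 253, so single ECGs fall at Cycles 3, 5, 7, 9 and 11 = 5. Share = 1/(4 + 5) = 1/9 = 11.1%.
- Earlier enrollees still on treatment at cutoff. The documents give no accrual period, so the lead over the last subject is assumed:

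| Assumed lead | Time on treatment | Cycle reached | Single ECGs | Share |
|---|---|---|---|---|
| 6 months | 14 × 30.4375 = 426.1 days | 21 | 10 | 1/14 = 7.1% |
| 12 months | 20 × 30.4375 = 608.8 days | 29 | 14 | 1/18 = 5.6% |
| 18 months | 26 × 30.4375 = 791.4 days | 38 | 18 | 1/22 = 4.5% |

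These are shares of the schedule, not effect sizes. Unscheduled ECGs would lower them. Footnote 13 also says that later-cycle ECGs are taken as clinically indicated, which sits awkwardly with the every-other-cycle schedule and makes the later denominators uncertain. The 1-in-4 count is unaffected.

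**Direction.** Dropping a value from a set can only lower its maximum or leave it unchanged, so any error understates worst-case ECG results.

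**The case against.** The strongest reply is that the exclusion is inferred. An ECG taken 1-4 hours after the first dose lies within the on-treatment period as SAP 3.5 defines it, and no sentence says outright that it falls outside. The same-day sentence points to SAP 3.4, whose ECG-specific wording should prevail over a general rule: a post-dose ECG is not baseline, so it must be on-treatment. SAP 2 (all data up to cutoff are included) and SAP 6.5.5 (which handles ECGs at nominal post-dose times) lean the same way. That reading is reasonable and is why the conflict is resolvable. But SAP 3.4 only selects the baseline value; it does not say that an unselected same-day ECG becomes on-treatment. The contrast in SAP 3.5 between adverse events and everything else points the other way.

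The second reply is that little is lost, and much of it stands. Three post-dose triplicates remain under either reading. A PR category is reached only with an increase of at least 50% (baseline below 200 msec) or at least 25% (baseline 200 msec or more), and protocol 1.2.3.3.3 predicts a low probability of PR reaching 200 msec at 100 mg QD. Every ECG is listed. Clinically significant findings, and results needing further testing or intervention, become adverse events (protocol 7.4.4 and 8.2.2), which count as on-treatment on Day 1. SAP 6.5.5 also calls for a description in the study report when a single reading in a triplicate reaches 500 msec but the mean does not. None of this restores a missing worst-case category to the tables.

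The tension with protocol 9.5.3, under which all ECGs are evaluated for safety, adds little. Listing is a form of evaluation, and protocol section 9 lets the SAP modify the protocol. The laboratory wording in SAP 6.5.3 shows inconsistent use of 3.4 but does not govern ECGs.

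**Conclusion.** The concern holds as a conflict within the SAP. Read literally, the same-day rule leaves one planned post-dose ECG time point per patient out of the summaries: 1 of 4 at 1-4 hours post-dose (25%), or about 5% to 20% of all scheduled ECGs after first dose in the cases worked above, the lower end resting on assumed accrual leads. The direction is known, because maxima are lowered or unchanged. The effect in msec or patients is not known. What remains at risk is a patient whose worst QTc, PR or QRS category occurs only at that time point. If the programmers already intend the inclusive reading, nothing is lost, but the SAP should say so. The primary ORR analysis is unaffected. The correction should be made, though its consequence is probably small.

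**What to change.** Add one ECG-specific sentence to SAP 3.5, for example:

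> *ECGs on the day of first dose are baseline only if taken pre-dose (by nominal time point, or by recorded time for unscheduled ECGs where available). The Cycle 1 Day 1 1-4 hour post-dose ECG, and any other ECG shown to be post-dose that day, is on-treatment and enters the Section 6.5.5 summaries.*

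Leave the date-based rule in place for laboratory and other assessments.

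The cost is one sentence and the matching programming rule. Scheduled ECGs need no new data, because footnote 13 already makes pre-dose and 1-4 hours separate time points. An unscheduled same-day ECG can be classified only if its clock time was recorded, and the documents do not say whether it is.
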